4.4 END-OF-STUDY DEFINITION

A participant is considered to have completed the study if he or she has completed the baseline assessment and the 6-month follow-up assessment.

5 STUDY POPULATION

5.1 INCLUSION CRITERIA

In order to be eligible to participate in this study, an individual must meet all of the following criteria:

1. Provision of signed and dated informed consent form
2. Stated willingness to comply with all study procedures and lifestyle considerations and availability for the duration of the study
3. Males; ages 45-75
4. Self-identify as Black or African American
5. Noncompliant with CRC screening recommendations via medical records review
6. Access to a smartphone

5.2 EXCLUSION CRITERIA

An individual who meets any of the following criteria will be excluded from participation in this study:

1. Lack of limited English literacy skills
2. Presence of colorectal cancer or a previous colorectal cancer diagnosis

5.3 LIFESTYLE CONSIDERATIONS

N/A

5.4 SCREEN FAILURES

Screen failures are defined as participants who consent to participate in this study but are not subsequently assigned to the study intervention or entered in the study. Re-screening is permitted if circumstances change.

5.5 STRATEGIES FOR RECRUITMENT AND RETENTION

Participants will be recruited by 2-3 community health workers employed by our partner medical clinic. The partner clinic serves Washington, DC communities east of the Anacostia River and are an integral part of the community with extensive outreach efforts including a needle exchange mobile van program and oral rapid HIV testing at DMV sites. Based on the clinic's wide range of services, it is likely that participants' health status will range from those who are healthy to those who are managing one or more chronic diseases or infections (e.g., Hepatitis C, diabetes, hypertension). Recruitment will occur at the partner clinic and in the surrounding community where outreach activities are conducted. Specifically, 2-3 community health workers will hand out palm cards to African American men in the primary care waiting rooms and at community outreach events (e.g., health fairs). The recruiters, as well as the text on the palm card, will instruct interested participants to contact the onsite field test coordinator for more information about the project and will provide the room number, a telephone number, and the hours during which the field test coordinator is available. We successfully used this strategy to recruit African American men from the same clinic for a recent randomized trial of a computer-based HIV behavioral intervention.

To maximize retention, this study will employ several techniques that have proven successful in previous research projects conducted at the clinic with similar populations. First, the onsite field test coordinator will collect as much contact information as the participant feels comfortable providing (e.g., additional phone numbers, email address, preference for calls v. text messages). This will include asking about secondary contacts – these are alternate phone numbers where the participant can be reached, such as the number of a parent, spouse, or friend. To protect participant's privacy, the field test coordinator will record how the project should be identified when calling each secondary contact (e.g., "the colorectal cancer project" v. "the phone study"). We have successfully retained participants whose personal phones were temporarily unavailable (e.g., the phone was broken or disconnected, the participant got a new number) using this strategy. Second, we will offer reminder texts or calls the day before a scheduled appointment. Third, if a participant misses a scheduled appointment, the field test coordinator will implement the retention protocol with the goal of rescheduling the missed appointment. Specifically, the field test coordinator will contact the participant via his preferred contact method the day of the missed appointment and – if he is not reached – every two business days thereafter for one week. If the participant is not reached within a week, the ISA field test coordinator will begin calling the alternate contacts' phone numbers. If the participant is not reached after calling each alternate contact once, the field test coordinator will continue contacting the primary number every two days for an additional week. If the participant is not reached after two weeks, the field test coordinator and the Principal Investigator will meet to determine whether additional contacts are warranted or if the participant should be categorized as "lost to follow up."

In general, retention rates for projects conducted at the clinic have been high. The clinic is well regarded in the community and many participants visit regularly for medical care or other services. We believe the proposed study will have similarly favorable retention rates.

6 STUDY INTERVENTION(S) OR EXPERIMENTAL MANIPULATION(S)

No text is to be entered in this section; rather it should be included under the relevant subheadings below.

6.1 STUDY INTERVENTION(S) OR EXPERIMENTAL MANIPULATION(S) ADMINISTRATION

No text is to be entered in this section; rather it should be included under the relevant subheadings below.

6.1.1 STUDY INTERVENTION OR EXPERIMENTAL MANIPULATION DESCRIPTION

m-CRCSi is an effective, affordable, and scalable intervention to increase CRC screening among African American men. The Health Belief Model (HBM) will guide intervention development. The HBM posits that a person is more likely to perform a health behavior when he: understands the seriousness of an illness (perceived severity) and feels there is a realistic chance he will develop it (perceived susceptibility), expects that the health behavior will reduce risks from the illness (perceived benefits) with relatively few costs (perceived barriers), is aware of the health behavior (cues to action), and believes he can perform it (self-efficacy). Theory-based assessments of these health beliefs will be used to tailor the intervention. It will also be targeted by contextualizing HBM constructs with the health beliefs and information needs of African American men and by integrating congruent imagery, language, and values.

Participants meet “William,” a Black health educator, who hosts five short video chapters: CRC basics; personalized screening guidance; colonoscopy deep-dive; stool-test options; and real-world roadblocks (cost, access, distrust, logistics) with practical workarounds. Content mixes host segments, expert Q&A ([name]), and men’s roundtables to normalize screening, name fears, and model solutions. After Chapter 1, a brief health history routes men to tailored messages: average-risk vs high-risk; unscreened vs up-to-date; under-45 paths; symptom prompts. Chapter 2 scripts change accordingly, then branch into colonoscopy vs stool-test education with concrete prep tips, tradeoffs, and “which test fits you” framing. A participant learns the basics, receives a personalized plan, selects a test that fits, uses reminders and resources to overcome barriers, and confirms screening via “SCREEN”—all with minimal clinic lift and high resonance.

Attention-control materials consist of a series of text messages including information and links to CDC-produced videos covering CRC risk, screening options, and general prevention. Over 8 weeks, users receive 16 text messages with either information about CRC or links to CDC-developed videos about CRC. These texts and videos include information about CRC, CRC screening tests, barriers and benefits to CRC screening, and other health-related beliefs about CRC.

6.1.2 ADMINISTRATION AND/OR DOSING

Participants in the intervention arm receive a fully automated, mobile program that blends short, pre-recorded video chapters with behaviorally informed SMS prompts. Delivery is remote and device-based (links arrive by text; videos open on the participant's phone), so all exposure occurs in participants' everyday settings rather than in clinic (video host "William," a health educator, introduces and guides the experience). The curriculum phase consists of a sequenced video pathway with five content areas: (0) Orientation/how-to; (1) CRC basics and screening rationale; (2) a tailored "Your Screening Plan"; (3) colonoscopy skills/support; and (4) stool-test skills/support, followed by (5) "Roadblocks" with practical workarounds. This structure (multiple brief videos per chapter) is scripted and enumerated in the master outline. A complete ("full-dose") curriculum exposure is defined as viewing the core chapter set (0–5) with the tailored branch in Chapter 2 (average- vs high-risk; screened vs unscreened) and the colonoscopy and/or stool-test micro-modules appropriate to that branch. Immediately after education, participants enter a Post-Education Screening Assistance (PESA) phase driven by SMS logic. This phase checks status, offers tips/resources, and schedules periodic reminders keyed to whether a colonoscopy or stool test is planned, scheduled, completed, or not planned. Example schedules include check-ins and supports at 2, 3, 5, 6, 8, 10, 12, 14 days and beyond, with the system extending supportive messaging out to roughly 16 weeks (e.g., 88, 94, 100, 108, and 116 days since the initial PESA trigger).

Curriculum frequency/intensity. Videos are brief (micro-learning format) and delivered via SMS links in sequence; the program advances if a user stalls, with nudges to keep momentum. The curriculum comprises multiple short videos across Chapters 0–5; for dose accounting, we treat each chapter as a "session," yielding ~5 sessions for a full curriculum dose (with additional sub-sessions in the tailored Chapter 2 branch and the chosen test-skills modules).

PESA frequency/intensity. After education, SMS prompts occur on a fixed timer and/or when users report milestones (e.g., "scheduled in 2–4 weeks," "don't know date yet," "planning to schedule"). Messages cluster early (2–10 days), then taper while extending for up to ~116 days if screening has not yet occurred.

Engagement prompts and escalations. If the post-education questionnaire is not completed within 5 days, targeted nudges are sent to re-engage and route the appropriate support stream.

There are **no live interventionists and no participant-to-participant interaction** after randomization. All contact is one-to-one, automated, and virtual: a pre-recorded health educator hosts the videos; the SMS engine personalizes cadence and content based on responses (e.g., keywords such as SCREEN) and branching logic. No face-to-face or group sessions are conducted.

Control arm receives 1–2 SMS per week for 8 weeks providing information about CRC and linking to CDC materials.

6.2 FIDELITY

No text is to be entered in this section; rather it should be included under the relevant subheadings below. This section refers to efforts made to confirm that the intervention is appropriately conducted by the interventionist(s). It is distinct from the content of Section 6.4, Study Intervention Adherence, which is intended to capture a study participant's adherence to an intervention.

6.2.1 INTERVENTIONIST TRAINING AND TRACKING

Timed text messages – called nudges – are sent to experimental participants at pre-specified intervals if they have not engaged with or completed a video chapter. After 7 days, an autodrop of the next chapter is triggered even if participants have not completed the previous chapter. Although no one “administers” the intervention content, study staff may assist with enrollment logistics and basic tech support. Staff will not advise on screening choices or alter message timing/content. If a participant becomes “stalled” (i.e., they have not engaged with intervention content in over 7 days and have not completed the intervention), an email message is sent to the study coordinator. The study coordinator then contacts the participant to inquire about any issues or questions and reinforce the importance of engaging with the intervention.

To ensure consistent delivery across arms, we will perform routine quality control (QC) checks using the SMS platform’s audit logs and dashboards. QC procedures include: (a) automated monitoring of send failures (hard/soft bounces) with daily review and same-day re-send or number verification; (b) timing-drift checks comparing scheduled vs. actual send times (tolerance ± 5 minutes for fixed-time sends; ± 24 hours for week-based sequences) with corrective action logged; (c) weekly link-uptime validation (HTTP status and redirect integrity) for all URLs in both arms, with broken links replaced from a preapproved list; and (d) parity audits to confirm equivalent contact frequency and timing windows across study arms. All QC activities are documented in an audit trail (issue, detection date, corrective action, verification). Responsibility: Study Technologist (daily automated checks) and Project Manager (weekly parity audit); oversight by the PI.

Control fidelity is tracked via delivery logs, weekly link checks, and audit reports confirming scheduled sends and link availability.

6.3 MEASURES TO MINIMIZE BIAS: RANDOMIZATION AND BLINDING

Participants will be assigned to conditions by an algorithm programmed into the computer-based research portal. Randomization will utilize a permuted-blocks randomization scheme. Blocks of size 4 and 6 will be used. Assignments within blocks will be random but balanced among the two conditions and the order of the blocks (4 vs 6) also will be random. This procedure will ensure that the number of participants randomized to each condition will be equal, that any imbalance among the conditions at any point during the recruitment and randomization will be modest, and that it will be very difficult to guess the assignment of the next participant. Because the intervention and control materials are inherently different, participants and research staff cannot be blinded to assignment. To limit bias, primary outcome ascertainment (MRR-verified receipt of CRC screening within 6 months) will be conducted by clinic staff who abstract electronic health records without reference to group assignment; two abstractors will review each record and reconcile discrepancies, providing an additional safeguard against bias.

6.4 STUDY INTERVENTION/EXPERIMENTAL MANIPULATION ADHERENCE

Participants’ adherence is tracked entirely through platform telemetry. During the curriculum phase, the SMS system records each linked video open and completion at the chapter/video level, issues time-based nudges when progress stalls (e.g., Day 2/4/6/7 rules for Chapter 1), and—if needed—auto-advances to the next assessment to preserve momentum. In the post-education phase, completion of the brief status questionnaire is monitored; automated reminders are sent at 2, 4, and 5 days if incomplete. Thereafter,

scheduled check-ins and resources continue on a fixed cadence (extending to ~116 days for noncompleters), and participant replies (including the keyword SCREEN) are logged as adherence signals and to close out the program when screening is reported.

Mandatory activities to remain an active participant are: consent, baseline questionnaire completion, randomization, and provision of a working mobile number (to enable delivery). All subsequent educational exposures (video views) and assessments are encouraged and tracked but not required for continued participation; the system's escalation (nudges/auto-drops) is designed to maximize exposure without removing participants for nonresponse.

Source records for adherence include the SMS platform logs (timestamps, message types, opens/completions, replies) and assessment completion flags. Optional activities available to participants (and tracked when used) include engaging the built-in reminder system and revisiting resources/videos; use is captured by link launches and elapsed time triggers.

No in-person visits are required for adherence. For transparency in reporting dose/exposure, we will summarize: number of curriculum videos delivered/opened, assessment completion and days-to-completion, number of SMS messages delivered and proportion eliciting a reply, days retained in the assistance stream, and whether/when screening was confirmed via SMS.

Control-arm adherence (e.g., link click-throughs or time on page) is not collected. To minimize participant burden and maintain parity with standard informational outreach, we verify delivery only, using SMS send logs. Primary analyses are intention-to-treat and do not rely on control exposure metrics.

6.5 CONCOMITANT THERAPY

N/A

6.5.1 RESCUE THERAPY

N/A

7 STUDY INTERVENTION/EXPERIMENTAL MANIPULATION DISCONTINUATION AND PARTICIPANT DISCONTINUATION/WITHDRAWAL

No text is to be entered in this section; rather it should be included under the relevant subheadings below.

7.1 DISCONTINUATION OF STUDY INTERVENTION/EXPERIMENTAL MANIPULATION

When a subject discontinues from the intervention but not from the study, remaining study procedures will be completed as indicated by the study protocol. If a clinically significant finding is identified (including, but not limited to changes from baseline) after enrollment, the investigator or qualified designee will determine if any change in participant management is needed. Any new clinically relevant

finding will be reported as an adverse event (AE). The data to be collected at the time of study intervention discontinuation will include the following: the reason(s) for discontinuing the participant from the intervention, and methods for determining the need to discontinue

7.2 PARTICIPANT DISCONTINUATION/WITHDRAWAL FROM THE STUDY

Participants are free to withdraw from participation in the study at any time upon request.

An investigator may discontinue a participant from the study for the following reasons:

- Lost-to-follow up; unable to contact subject
- Participant withdraws consent for further participation and/or data use.
- Participant texts “STOP” to the experimental intervention phone number.
- Safety concerns: any SAE or AE judged related to participation that warrants removal, per the Data and Safety Monitoring Plan and IRB reporting rules.
- Ineligibility discovered post-enrollment, duplicate enrollment, or other protocol violations that compromise data integrity.
- Investigator decision that continued participation poses undue burden or risk (e.g., credible threats of harm), consistent with IRB policies.

The reason for participant discontinuation or withdrawal from the study will be recorded on a dedicated Case Report Form (CRF). Participants who withdraw or are discontinued after randomization will not be replaced; enrollment continues until the target sample size is reached.

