- **Follow-up questionnaire:** repeat of key psychosocial measures to explore mechanisms and acceptability.

Outcome definitions (non-safety)

- **CRC screening completion:** Documentation in the medical record or self-report of colonoscopy, FIT, FIT-DNA, CT colonography, or flexible sigmoidoscopy performed within the 6-month window (plus any pre-specified grace period).

- **Exposure/dose metrics:** Number of SMS delivered; proportion eliciting a response; number/proportion of videos opened by chapter; completion of the immediate post-education questionnaire; and elapsed days in PESA until closeout.

Administration, scoring, and data quality

- **Administration.** All questionnaires are administered via telephone.
- **Scoring.** Multi-item scales are scored per codebook (sum or mean of valid items; higher scores reflect greater endorsement or knowledge, as defined). Missing-data rules (e.g., minimum items required) are pre-specified.
- **Data capture.** Survey responses and SMS telemetry are time-stamped and stored on the study platform; MRR uses standardized abstraction forms with dual review and reconciliation.

Qualified personnel

- **MRR:** Conducted by trained study staff (e.g., clinic research coordinators) using a standardized abstraction guide; complex clinical ambiguities are adjudicated by a qualified clinician (e.g., physician or advanced practice provider).
- **Telephone-based assessment:** Conducted by trained study staff.

Use of existing clinical data and HIPAA

The study uses existing medical charts to verify CRC screening. HIPAA, applicable federal/state laws, and local institutional requirements are followed. MRR variables include test type and date (and result if available). No central lab is used; no CLIA-covered testing is performed by the study.

Standard of care procedures

All screening tests are ordered and performed as part of routine clinical care, independent of the research team. The study does not alter clinical pathways, rescue therapy, or provider decision-making.

Results returned to participants

Participants receive general educational messages and resource links through the intervention or control SMS sequences. The study does not generate new clinical test results; any clinical results (e.g., from a colonoscopy) are communicated by the healthcare system per usual care.

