9.1 STATISTICAL HYPOTHESES

- Primary Endpoint(s):

We hypothesize that, compared to participants who receive standard educational materials via SMS (control), participants who receive the tailored mobile video+SMS intervention (m-CRCSi) will have a higher proportion completing any guideline-concordant colorectal cancer (CRC) screening within 6 months post-randomization. Alternatively, our null hypothesis is that there will be no difference between arms in screening completion at 6 months.

- Secondary Endpoint(s):

Self-reported proxy screening composite (6 months):

We hypothesize that the intervention arm will report a higher rate of any guideline-concordant CRC screening by 6 months than the control arm; the null hypothesis is that there will be no difference between arms.

CRC knowledge (baseline→6 months):

We hypothesize that intervention participants will show greater improvement in CRC knowledge from baseline to 6 months than control participants; the null hypothesis is that there will be no difference in change between arms.

Perceived susceptibility and severity (baseline→6 months):

We hypothesize that intervention participants will report greater increases in perceived susceptibility and severity from baseline to 6 months than control participants; the null hypothesis is that there will be no difference in change between arms.

Perceived benefits and barriers for colonoscopy and stool testing (baseline→6 months):

We hypothesize that intervention participants will report greater increases in perceived benefits and greater decreases in perceived barriers from baseline to 6 months than control participants; the null hypothesis is that there will be no difference in change between arms.

Medical trust (baseline→6 months):

We hypothesize that intervention participants will report greater increases in trust in the medical profession from baseline to 6 months than control participants; the null hypothesis is that there will be no difference in change between arms.

Self-efficacy (overall; colonoscopy; stool test) and advocacy (baseline→6 months):

We hypothesize that intervention participants will demonstrate greater improvements from baseline to 6 months than control participants; the null hypothesis is that there will be no difference in change between arms.

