9.3 POPULATIONS FOR ANALYSES

Because randomization carries the expectation of creating treatment groups equivalent with respect to known and unknown prognostic factors, removing randomized participants from the analysis runs the risk of tampering with this balance and introducing bias into the treatment comparisons. As a result, an intention-to-treat analytic approach will be followed such that all participants randomized into the study will be included in all analyses irrespective of protocol violations post randomization. Even with our best efforts, we can expect some missing data. For the primary outcome, missing data will be limited to cases where we are unable to complete an MRR review. Because we will have medical releases for all participants on our primary outcome, very little missing data is anticipated. For secondary measures, missing data will consist of those who fail to complete the 6-month follow-up survey. We will conduct an initial evaluation of missingness by performing a series of logistic regression analyses where the indicator of missing data is the outcome and potential explanatory variables (e.g., condition, screening status, demographic characteristics) serve as predictors. We will then use imputation to manage missing data.

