9.4.2 ANALYSIS OF THE PRIMARY ENDPOINT(S)

For the primary outcome, if any missing data is identified, both negative and multiple imputation methods

will be used to estimate CRC screening completion. This approach to missing data was successfully used by Vernon and colleagues (Kinney et al, 2014; Steffen et al, 2015). Negative outcome imputation will assume that if there was no MRR-verified CRC screening, the procedure did not occur. Multiple imputation will be based on experimental condition, age at baseline, income, health insurance coverage, and any other covariates predictive of missingness in the imputation model. Twenty imputed datasets will be used to provide a combined estimate for missing values. We will employ SAS PROC MI and SAS PROC MIANALYZE, Version 9.4, to implement these imputation procedures. We will also conduct a complete case analysis including only those participants with a known primary outcome.

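### Section 7.2 makes a STOP text to the experimental number a ground for leaving the study, with no control-arm counterpart and in conflict with Sections 2.3.1, 6.4 and 7.1

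*Combined protocol and SAP*

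**What the plan says.** Section 7.2 sets out reasons for which an investigator may discontinue a participant from the study. One is "Participant texts “STOP” to the experimental intervention phone number". Withdrawal of consent is a separate item in the same list. No item covers a STOP text sent by a control participant, yet Section 6.1.2 states: "Control arm receives 1–2 SMS per week for 8 weeks providing information about CRC and linking to CDC materials". Section 6.1.1 likewise describes 16 control texts over 8 weeks.

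Three other places treat stopping the messages differently:

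- Section 2.3.1 tells participants, without distinguishing arms, that they may opt out of the intervention and its messages. It does not mention leaving the study.
- Section 6.4 limits the mandatory activities to consent, baseline questionnaire, randomisation and a working mobile number. Video views and later assessments are encouraged but are not a condition of staying in.
- Section 7.1 says: "When a subject discontinues from the intervention but not from the study, remaining study procedures will be completed as indicated by the study protocol".

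On outcomes, Section 8.1 says "All questionnaires are administered via telephone". Its definition of screening completion accepts either the medical record or self-report. Section 9.1 also lists a self-reported screening composite as a secondary endpoint: "We hypothesize that the intervention arm will report a higher rate of any guideline-concordant CRC screening by 6 months than the control arm".

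**The concern.** One act, texting STOP, can end study participation in the experimental arm and has no stated consequence in the control arm. No section says whether 7.1 or 7.2 governs it. If 7.2 is applied and follow-up ends, surveys are lost after randomisation under a rule that only one arm can trigger.

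The men lost need not resemble those who stay. On the account in Section 6.1.2, assistance texts run for up to about 116 days while screening has not occurred, against 8 weeks of control texts. (The table in Section 1.3 marks the arms differently.) Men who remain unscreened may therefore have longer in which to send STOP.

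At stake are knowledge, health beliefs, medical trust, self-efficacy, the self-reported composite, and any screening found only by self-report. Because the survey is by telephone, ending the texts does not in itself prevent it. The loss would come from the rule.

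**Working it through.** **The plan's own figure.** The only stated number bearing on follow-up loss is the attrition allowance in Section 9.2: 154 / (1 − 0.20) = 192.5, rounded up to 193, which reproduces. It is a single rate for both arms. No STOP rate is given anywhere, so everything below is an assumption shown as a range.

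**Inputs.** Arm sizes are 63 experimental and 65 control (Section 1.2). From Section 9.2 come the yardstick effect d = 0.27 for self-efficacy and the planning rates of 34% (33/98) and 19% (18/94). Assumed: q, the share of experimental men who lose the survey through this ground, from 0 to 0.20; and δ, the difference between them and the completers that imputation does not explain, from −0.5 to +0.5 SD.

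**Scale outcomes.** Shift in the arm difference = q × δ.

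| q | men (63q) | largest shift | share of 0.27 |
|---|---|---|---|
| 0 | 0 | 0 | 0% |
| 5% | 3.2 | ±0.025 SD | 9.3% |
| 10% | 6.3 | ±0.05 SD | 18.5% |
| 20% | 12.6 | ±0.10 SD | 37.0% |

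For comparison, the standard error of the arm difference at q = 20% is √(1/50.4 + 1/65) = 0.188 SD, and 0.10/0.188 = 0.53. The largest case is about half of one standard error.

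**Self-reported composite, observed respondents, before imputation.** Bias in the experimental rate = q(p − r)/(1 − q), where p is the arm's true rate and r the rate among the men lost.

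- p = 19%, q from 5% to 20%: +1.0 to +4.75 points if r = 0; 0 if r = p; −1.0 to −4.75 if r = 2p.
- p = 34%: +1.8 to +8.5 points, 0, and −1.8 to −8.5 for the same three cases.

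Section 9.4.3 plans multiple imputation for secondary outcomes by the procedure of Section 9.4.2: "Multiple imputation will be based on experimental condition, age at baseline, income, health insurance coverage, and any other covariates predictive of missingness". The bias falls as far as those covariates explain who is lost. If they explain none of it, the figures stay about the same.

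**Self-report part of the screening definition.** If a share u of screened men is found only by self-report, the experimental rate is understated by p × u × q. With p = 0.34, this is 0.34 × 0.10 × 0.05 = 0.17 points at the low end and 0.34 × 0.30 × 0.20 = 2.04 points at the high end. With p = 0.19 the corresponding values are 0.10 and 1.14. The values of u are assumed.

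**MRR-verified primary outcome.** Section 9.3 says: "For the primary outcome, missing data will be limited to cases where we are unable to complete an MRR review". Section 10.1.1.2 has men told that their records will be checked again at the end of the study. If that is done for all randomised men, the effect is 0.

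**The case against.** The strongest reply is that survey loss is the less natural reading. Sections 2.3.1 and 6.4 point to opt-out as leaving the messages only, and Section 7.1 then keeps the man in follow-up. The ground in 7.2 is permissive, so it may never have been used. Control men can also withdraw on request, and the undue-burden ground in 7.2 covers both arms. A man who texts STOP might have been lost anyway, so q is not shown to be net extra loss. The upper value of q equals the whole all-cause attrition allowance, and a residual 0.5 SD after imputation has no support in the documents. Enrolment also appears complete, judging by Sections 1.2, 2.1 and 4.1.

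Most of this stands, and it limits the size of the point. It does not remove the conflict. Section 7.2 is the only place that names STOP, it does so under leaving the study, and it does so for one arm. Sections 2.3.1 and 6.4 do not mention STOP and so cannot settle which rule applies.

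A reader might also infer that staff could apply the ground selectively, since "participants and research staff cannot be blinded to assignment". That adds little. Every man subject to the ground is in the experimental arm, so knowing the assignment cannot distinguish among them. The asymmetry comes from the wording.

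**Conclusion.** The point holds as an arm-specific discontinuation ground that conflicts with three other sections. If used, it gives the experimental arm one more route to losing the 6-month survey. It bears mainly on survey-based secondary outcomes, and on the screening outcome only as far as self-report counts towards it. The loss may be zero. The illustrated range, 0 to ±0.10 SD on a scale outcome, rests wholly on assumed values of q and δ.

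Two stronger readings are not supported:

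- That differential attrition is built into the trial. The ground is optional and no count of STOP texts is given.
- That the primary result is biased, or biased in a known direction. The MRR-verified outcome is untouched if MRR is done for everyone. Even if MRR were also stopped for these men, the direction would depend on their screening rate. At p = 19% and q = 20%, complete-case bias and negative-imputation bias (−q × r) are +2.4 and −1.9 points if r = 9.5%, but −4.75 and −7.6 if r = 38%.

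The consent pages and the Manual of Procedures were not available and may say more about how STOP is handled.

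**What to change.** Reconcile Section 7.2 with Sections 2.3.1, 6.4 and 7.1:

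- Remove the STOP item from 7.2 and record STOP, in either arm, as message opt-out under 7.1.
- State in 7.2 and 7.3 that MRR is completed for every randomised man unless he withdraws consent for data use, and that the 6-month survey is still offered unless he withdraws from participation.
- For men already discontinued, complete any outstanding MRR before the linking file is deleted (Section 10.1.3).
- Report STOP texts and Section 7.2 discontinuations by arm. Reasons for discontinuation are already recorded on a dedicated form, so those counts should be readily available.

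The cost is minor wording and a few chart reviews that are already authorised. Surveys already missed cannot be recovered. For those men the gain is limited to a confirmed MRR outcome and counts that show readers whether the asymmetry mattered.
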